## **Objective:**

**Primary:** To determine the effect of an alcohol-free beer with low glycemic index carbohydrates (isomaltulose) and a resistant maltodextrin, comparing to an alcohol-free beer with regular composition, on glycemic metabolism (glucose, glycated hemoglobin, insulin and HOMA index) in subjects with recently diagnosed diabetes mellitus and overweight or obesity.

**Secondary:** To determine the effect of an alcohol-free beer with low glycemic index carbohydrates (isomaltulose) and a resistant maltodextrin, comparing to an alcohol-free beer with regular composition, on: a) lipid profile (total cholesterol, LDL cholesterol, HDL cholesterol, triglycerides and apolipoproteins A and B); b) body weight and waist circumference; c) inflammatory biomarkers (C reactive protein); d) intestinal microbiota in a subgroup of participants.

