### **Study Detailed Description:**

The study involves a nutritional intervention with a controlled, double-blind, randomized, cross design. It includes 44 healthy subjects with a total duration of 20 weeks with a "wash-out/stabilization" period for 2-4 weeks before randomization. Subjects are randomized in two groups: (1) those who begin drinking 2 alcohol-free beers (33 cl each one) that are enriched in a resistant maltodextrin and isomaltulose during 10 weeks and continue drinking 2 alcohol-free beers (33 cl each one) with regular composition during the next 10 weeks following; (2) those who will follow the same previous intervention but in reverse, beginning with standard alcohol-free beer for 10 weeks, followed by resistant maltodextrin and isomaltulose-enriched beer for the remaining 10 weeks. There is a washout period between both phases to facilitate adherence to nutritional intervention, since we consider that a period of 20 consecutive weeks could be difficult to assume for the participants. Participants and the research team are "blind" to the type of beer that subjects are taking in each phase. Only one person of the company that provide beers, which does not directly participate in the clinic visits or in the analysis of the data, is aware of this information. Clinical staff performed the randomization based on a computerized method.

Among those subjects included in the study, microbiota sub-study is proposed which require a specific authorization within informed consent. Among all subjects that are included in this substudy and that have completed the whole nutritional intervention, 10 subjects (5 from each randomized group) will be selected to microbiota determination.

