### **Statistical analysis plan**

The sample size was established by taking as main outcome variable the change of glucose concentration, whose clinical variability is estimated at 16 mg/dL in pre-diabetic population. This is the estimated value based on the epidemiological study carried out in Spanish population (PREDIMED) (Estruch R et al. N Engl J Med 2013;368:1279-90). It was expected to find a difference of 12 mg/dL in glucose levels between two intervention

arms. It was established a confidence level ( $1-\alpha$ ) of 95% (bilateral  $Z\alpha = 1,960$ ) and 90% of statistical power ( $1 - \beta$ ) (bilateral  $Z\beta = 1,282$ ), by obtaining a sample size of 37 subjects. It was estimated a 25% loss rate, so final sample was 44 subjects.

Different alcohol-free beers effects on study outcomes will be evaluated by repeated measures ANOVA or the Friedman test, as appropriate. When significant differences are detected, multiple comparisons will be made by using the Bonferroni correction for normally distributed variables or the Wilcoxon test for paired samples for variables with a skewed distribution. Treatment order will be entered in all models as an additional factor. Data will be presented as means ( $\pm$ SD) for continuous variables or medians and interquartile ranges (IR) for those with a skewed distribution). Statistical analysis will be processed using the software SPSS (version 24.0; SPSS, Chicago, Illinois, USA), using a significance level of  $P < 0,05$ .

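### Skewed outcomes go to rank tests that cannot carry treatment order, and if the two beers are the compared levels, a sign test decides whether Wilcoxon is run

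*Combined protocol and SAP*

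**What the plan says.** All the relevant rules stand in the second paragraph of the Statistical analysis plan.

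- First test: "Different alcohol-free beers effects on study outcomes will be evaluated by repeated measures ANOVA or the Friedman test, as appropriate".
- Second step: "When significant differences are detected, multiple comparisons will be made by using the Bonferroni correction" for normal variables, "or the Wilcoxon test for paired samples for variables with a skewed distribution".
- Order: "Treatment order will be entered in all models as an additional factor".

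The sample-size paragraph was built by "taking as main outcome variable the change of glucose concentration". The primary objective also lists insulin and the HOMA index; triglycerides and C reactive protein are secondary. For the microbiota sub-study, "10 subjects (5 from each randomized group) will be selected to microbiota determination". On allocation the plan says only that "Clinical staff performed the randomization based on a computerized method"; it does not say whether the sequences are kept equal in size.

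The plan does not say which measurements form the columns of the Friedman test. It names no transformation, and no rank method that could carry order.

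**The concern.** The order sentence shows an intention to adjust everything, but the two tests named for skewed outcomes have no place for a between-subject factor. If that sentence is read as covering the ANOVA only, the contradiction goes, but skewed outcomes then have no order or period adjustment at all.

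The sequence of tests adds a second problem. Wilcoxon is reached only after a significant Friedman test. With two columns, Friedman uses only the direction of each subject's difference and ignores its size, so it can stop a beer effect that Wilcoxon would have found.

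At stake are the outcomes judged skewed. Insulin, HOMA, triglycerides, C reactive protein and bacterial counts are plausible candidates, but that is an assumption: the plan provides for skewed variables without listing them. Glucose change is affected only if it is judged skewed.

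**Working it through.** **Inputs.** From the Statistical analysis plan: SD 16 mg/dL, difference 12 mg/dL, Z values 1.960 and 1.282, 37 evaluable subjects, 44 recruited, 25% loss. The stated 37 follows from 2 × (1.960 + 1.282)² × 16² / 12² = 37.4. The lower sample size used here is 44 × 0.75 = 33. The SD of a between-beer difference in change is 16 × √2 = 22.6 if the two changes are uncorrelated, and 16 × √(2 × 0.6) = 17.5 at correlation 0.4. Correlations, period effects, sequence splits and distribution shapes are assumptions; the documents give none.

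**What the paired tests do with a period effect.** Let τ be the beer effect, and π the phase 2 minus phase 1 difference in mean change. A subject's difference (modified minus regular) is centred on τ + π if regular beer came first and on τ − π if it came second. Pooling them without order has two effects.

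- The centre moves to τ + π × (difference in sequence sizes)/n. For π = 11 this is a shift of 11 × 1/37 = 0.3 mg/dL at a 19/18 split and 11 × 11/37 = 3.3 mg/dL at 24/13.
- With near-equal sequences, the variance grows by about π². For π = 11 the SD rises from 22.6 to √(512 + 121) = 25.2; for π = 5, to √(512 + 25) = 23.2.

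If phase 2 minus phase 1 differences are compared between the sequences instead, their centres are π + τ and π − τ. The contrast is 2τ and the period effect cancels.

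**Friedman with two columns.** The statistic is (n₊ − n₋)²/n, the squared sign-test z, compared with 3.84.

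- n = 10: 9 to 1 gives 64/10 = 6.4; 8 to 2 gives 36/10 = 3.6. So 9 of 10 are needed.
- n = 33: 23 to 10 gives 169/33 = 5.1; 22 to 11 gives 3.7.
- n = 37: 25 to 12 gives 169/37 = 4.6; 24 to 13 gives 3.3.

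**Power lost to the Friedman step** (simulation, no period effect):

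| Differences | n | Friedman then Wilcoxon | Wilcoxon alone |
|---|---|---|---|
| Normal, 12 mg/dL, SD 22.6 | 33 | 0.60 | 0.82 |
| Same | 37 | 0.70 | 0.87 |
| Lognormal (within CV 25%, between CV 60%, beer ratio 0.75) | 33 | 0.60 | 0.79 |
| Same | 37 | 0.69 | 0.83 |
| Laplace (heavy-tailed) | 33 | 0.84 | 0.91 |
| Same | 37 | 0.90 | 0.94 |

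For normal data, even sample sizes between these lose about 13 to 15 points. At n = 10 (5 per sequence, standardised difference 1.0), power is 0.52 for Friedman, 0.79 for exact paired Wilcoxon and 0.68 for the exact rank-sum test.

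**Power lost to the missing order adjustment** (ungated paired Wilcoxon against rank-sum on period differences, normal, 12 mg/dL, SD 22.6, near-balanced): about 0 to 2 points at a 5 mg/dL shift and roughly 4 to 10 at 11 mg/dL, depending on which sequence holds the odd subject. In the lognormal case at n = 33, phase-2 end values 20% lower give 0.66 against 0.72; 20% higher give 0.81 against 0.81.

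**Type I error of the two-step route** (both tests significant, SD 17.5 to 22.6): about 0.025 with no shift. With shifts of 5 and 11 mg/dL it is at most 0.030 at 22/15 and at most about 0.043 at 21/12. At 24/13 it is 0.033 to 0.038 with a 5 mg/dL shift and 0.05 to 0.07 with 11 mg/dL. Rank-sum stays near 0.05 throughout.

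**The case against.** **Levels.** The sign-test result needs two Friedman columns. There are three visits per phase, and a Bonferroni step makes sense only with more than two levels, so all visits may have been meant. This stands as a reason to state the levels. It does not rescue the plan: Friedman over visits tests for differences among visits, not between beers, and still omits order. The sentence on beer effects points to the two beers.

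**Size.** The power loss depends on the shape of the data. With between-subject CV of 150% to 250% it falls to 9 to 15 points, and for some heavy-tailed differences it almost vanishes. The 9-of-10 rule assumes no ties: with four tied subjects, 6 of 6 in one direction gives 36/6 = 6.0, P = 0.014. Both limits stand.

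**False positives.** A reader might infer that leaving order out inflates the type I error. Paired Wilcoxon on its own does reach 0.097 to 0.119 at a 24/13 split with an 11 mg/dL shift, and Friedman on its own 0.083 to about 0.10. The plan, however, runs Wilcoxon only after a significant Friedman test, which brings this down to 0.05 to 0.07. Such a split of 37 cannot arise from 22/22 allocation of 44; with unrestricted randomisation a split at least that uneven has probability about 0.10. Averaged over random 1:1 order, even Wilcoxon alone shows no inflation. The stabilisation period, the washout and the baseline visit in each phase may also limit period effects, though they do not exclude them.

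**Normal outcomes.** A reader might also infer that they lack period adjustment. They do not if order is a between-subject factor with its beer-by-order term, because in a two-sequence crossover that term is the period effect. The plan only needs to say so.

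**Conclusion.** The concern holds for outcomes judged skewed. Their planned tests cannot include treatment order, on any reading of the plan. That much rests on the text alone.

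The larger cost is conditional. If the two beers are the Friedman levels, requiring a significant sign test before Wilcoxon loses about 13 to 22 power points at n = 33 to 37 for normal or moderately skewed differences and about 4 to 7 for Laplace differences. The missing order adjustment is a smaller matter: with near-balanced sequences it makes the rank tests conservative, with little power lost for modest shifts. The 11 mg/dL shift is an upper case, close to the whole planned effect of 12.

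The documents do not support a claim of material type I error inflation under the two-step route, nor a claim that the glucose comparison itself is compromised. The plan should be corrected before analysis, chiefly to protect power and to make the adjustment it promises possible.

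**What to change.** Replace Friedman and the conditional Wilcoxon test for the beer comparison.

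- List the positive skewed outcomes in advance. Analyse log(end/baseline) per phase in the same order-adjusted crossover analysis as the other outcomes, and report the beer ratio with its 95% confidence interval.
- Where ranks are still needed, such as values below an assay limit or zero counts, compare within-subject period differences in change between the two sequences by the Wilcoxon rank-sum test, using the exact version for the 10-subject sub-study.
- Drop the multiple-comparison step for the two-beer contrast.
- For normal outcomes, state that the test is the between-beer difference in within-phase change, with order as a between-subject factor and the beer-by-order term. Order as a main effect alone would leave the beer test equal to an unadjusted paired t-test.

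This needs no new data, only revised wording and minor SPSS work. Log results are read as ratios, and rank-sum gives a less direct effect estimate. With no period effect, rank-sum loses under 1 power point against ungated paired Wilcoxon at n = 33 to 37 with balanced sequences, about 2 to 4 points at splits from 22/15 to 24/13 or 21/12, and about 11 points at n = 10 (0.68 against 0.79), where it still exceeds Friedman (0.52).

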### **Brief Summary:**

This a controlled, double-blind, randomized, cross designed study to determine the effect of an alcohol-free beer with low glycemic index carbohydrates (isomaltulose) and a resistant maltodextrin, comparing to an alcohol-free beer with regular composition, on glycemic metabolism (glucose, glycated hemoglobin, insulin and HOMA index) in subjects with recently diagnosed diabetes mellitus and overweight or obesity. We include 44 subjects who are randomized to consume for 10 weeks: a) two alcohol-free beers with regular carbohydrates composition per day; b) two alcohol-free beers with modified carbohydrates composition per day. Those subjects randomized to begin with A beer

during 10 weeks will change to B beer during the second phase for 10 weeks and vice versa. There is a 4-8 weeks wash-out period between two phases.

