### **Study visits:**

1. Prescreening visit: Inclusion and exclusion criteria assessment and blood collection if glucose or glycated hemoglobin is not available in previous 3 months. Healthy dietary and physical activity counselling is provided by a nutritionist; it should be maintained during all study. Baseline visit is scheduled in 2-4 weeks after lifestyle stabilization.

2. Baseline phase 1 visit: Clinical, biochemical, dietary, physical activity and anthropometric data are assessed. Computer-based randomization is performed. Alcohol-free beer (A or B according to randomization procedures) for the next 10 weeks is delivered to the participant who has to consume two per day. A nutritionist emphasizes healthy lifestyle counselling to the participant. A feces sample is collected if subjects accept to be included in microbiota sub study.
3. Intermediate phase 1 visit: Clinical, biochemical, dietary, physical activity and anthropometric data are assessed. Satiety after alcohol-free beer consumption is measured by a validated questionnaire. A nutritionist emphasizes healthy lifestyle counselling to the participant.
4. End of phase 1 visit: Clinical, biochemical, dietary, physical activity and anthropometric data are assessed. Satiety after alcohol-free beer consumption is measured by a validated questionnaire. A nutritionist emphasizes healthy lifestyle counselling to the participant. A wash-out period of 4-8 weeks is scheduled before the next phase start. A feces sample is collected if subjects accept to be included in microbiota sub study.
5. Baseline phase 2 visit: Clinical, biochemical, dietary, physical activity and anthropometric data are assessed. Alcohol-free beer (A or B: if subjects consumed alcohol-free beer A, he/she change to alcohol-free B and vice versa) for the next 10 weeks is delivered to the participant who has to consume two per day. A nutritionist emphasizes healthy lifestyle counselling to the participant. A feces sample is collected if subjects accept to be included in microbiota sub study.
6. Intermediate phase 2 visit: Clinical, biochemical, dietary, physical activity and anthropometric data are assessed. Satiety after alcohol-free beer consumption is measured by a validated questionnaire. A nutritionist emphasizes healthy lifestyle counselling to the participant.

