7. End of phase 2 visit: Clinical, biochemical, dietary, physical activity and anthropometric data are assessed. Satiety after alcohol-free beer consumption is measured by a validated questionnaire. A nutritionist emphasizes healthy lifestyle counselling to the participant. A feces sample is collected if subjects accept to be included in microbiota sub study.

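### The SAP does not say which contrast establishes a beer effect; if its overall test runs across visits, that test and its within-beer follow-ups respond to changes shared by both beers

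*Combined protocol and SAP*

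**What the plan says.** The primary objective is comparative: the modified beer is studied "comparing to an alcohol-free beer with regular composition, on glycemic metabolism". Each participant takes both beers: "We include 44 subjects who are randomized to consume for 10 weeks" on one, then 10 weeks on the other. Between them, "There is a 4-8 weeks wash-out period between two phases".

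Under Study visits, biochemistry is assessed at baseline, intermediate and end visits of each phase, so there are six measurements per person. At prescreening, "Healthy dietary and physical activity counselling is provided by a nutritionist; it should be maintained during all study". At each of items 2 to 7, "A nutritionist emphasizes healthy lifestyle counselling to the participant". Before phase 1 there is a short settling period: "Baseline visit is scheduled in 2-4 weeks after lifestyle stabilization".

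The Statistical analysis plan then says: "Different alcohol-free beers effects on study outcomes will be evaluated by repeated measures ANOVA or the Friedman test, as appropriate". The next sentence is the follow-up rule: "When significant differences are detected, multiple comparisons will be made by using the Bonferroni correction for normally distributed variables", with the paired Wilcoxon test for skewed variables. Treatment order is to enter every model. The section does not say whether the repeated factor is beer, visit or both, or which pairs the follow-up compares.

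**The concern.** A comparison of two beers is a single contrast. It needs no overall test, leaves nothing to follow up, and gives Bonferroni nothing to correct. The rule has work to do only if the repeated levels are visits or beer-by-visit cells.

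If they are, the first test asks whether anything differs among the six cells, and the follow-up pairs include baseline to end within each beer. Those changes mix the beer with everything else that moves over 10 weeks: the repeated counselling, the natural course, and any regression to the mean still under way after entry on raised glucose or HbA1c. Bonferroni does not help, because it controls multiplicity and not confounding. The stabilisation and wash-out intervals are free of study beer, but neither is a randomised control, and counselling is given at both ends of the wash-out.

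The practical danger is a report that the modified beer lowered glucose and the regular beer did not, because one before-after test passed and the other missed. That does not answer the objective, and nothing in the plan rules it out.

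**Working it through.** **Inputs from the documents.** Expected difference 12 mg/dL, SD 16 mg/dL, two-sided z = 1.960, power z = 1.282, 37 evaluable subjects (Statistical analysis plan); six assessments (Study visits).

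**The plan's own figure.** 2 × (16 × (1.960 + 1.282) / 12)² = 37.4, which agrees with the stated 37. I use 37 completers below.

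**Assumptions not in the documents.** 16 mg/dL is the SD of one phase change, so the visit-level SD is 16/√2; visits are independent given the person; the wash-out lasts 6 weeks; there is no beer difference; and glucose falls by 3, 5 or 8 mg/dL per phase under both beers. Three shapes were tried: the fall reverses in the wash-out, continues steadily through all 26 weeks, or levels off after phase 1.

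**One within-beer test, by formula.** For a shared fall of 6 mg/dL, the standard error of the mean change is 16/√37 = 2.63, so the noncentrality is 6/2.63 = 2.28. A paired t-test is then significant with probability 60% at 0.05 and 32% at 0.05/6 (Bonferroni for six pairs). The two beers use separate visits, so if the fall is the same in each phase, exactly one beer passes the six-pair threshold in 2 × 0.32 × 0.68 = 44% of trials before any gate.

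**Non-parametric route, simulated.** Friedman on the six beer-by-visit cells; if significant, Wilcoxon baseline to end within each beer at P<0.05, since the plan attaches Bonferroni only to normally distributed variables.

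| Result, by shape of the shared fall | 3 mg/dL | 5 mg/dL | 8 mg/dL |
|---|---|---|---|
| Friedman significant: reverses | 16% | 41% | 87% |
| Friedman significant: steady | 14% | 33% | 70% |
| Friedman significant: levels off | 6% | 12% | 23% |
| Then exactly one beer significant: reverses | 11% | 25% | 21% |
| Then exactly one beer significant: steady | 9% | 17% | 12% |
| Then exactly one beer significant: levels off | 3% | 7% | 14% |

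With no trend, Friedman is significant in about 5% of trials and exactly one beer in about 2%. The share with exactly one beer can drop at larger falls because both beers then become significant. Repeat runs agreed to within about 3 percentage points.

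**Parametric route, simulated.** Repeated measures ANOVA, then six-pair Bonferroni, steady fall of 0, 3, 6, 9 or 12 mg/dL per 10 weeks: the overall test is significant in 5%, 16%, 54%, 87% and 99%; it is followed by at least one significant within-beer change in 1%, 8%, 45%, 86% and 99%, and by exactly one in 1%, 7%, 35%, 31% and 8%. If the fall comes early and levels off (6 or 12 mg/dL by week 10), at least one within-beer change is significant in 10% and 48%.

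**Between-beer contrast.** For each person, take the change under the modified beer minus the change under the regular beer, then average the two sequence means with equal weight, which is the order adjustment. It is significant in about 5% of trials at every trend size and shape. The adjustment matters: with sequences of 24 and 13 and an early 12 mg/dL fall, the same difference tested without order gives about 9%, and with order about 5%.

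**The case against.** The strongest reply is that the plan already aims at the right contrast. The objective is comparative, the stated target of the test is the effect of the beers, the sample size rests on a difference in glucose change between arms, and order enters every model. An ANOVA with beer and visit as within-person factors also fits the text, and its beer-by-visit term is built from between-beer differences in change. The multiple-comparison sentence may be generic. Nowhere does the plan say that a beer effect will be concluded from a before-after change.

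Much of this stands. The visit-based test is an inference. Counselling is the same under both beers in a randomised, double-blind crossover, so it is not a design flaw. What the reply does not supply is a named contrast. It also does not cover the skewed branch: a Friedman test over six cells cannot isolate a beer effect, and neither Friedman nor Wilcoxon can take the promised order factor.

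A reader might also infer that chance alone would show exactly one beer to be significant in a third to a half of trials. Counting uncorrected before-after tests, without first requiring a significant overall test, does give 32%, 50% and 28% for falls of 3, 5 and 8 mg/dL. Those figures do not follow the plan's two-step rule, they assume that the fall reverses in the wash-out, and roughly 9 to 10% would occur with no trend at all.

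**Conclusion.** The concern holds as a gap in specification with a demonstrable consequence. The SAP does not commit to the between-beer contrast, and the procedure it describes, read in the way that gives it work to do, can become significant because of changes common to both beers. Over the assumed falls of 3 to 8 mg/dL, the six-cell Friedman test is significant in 6% to 87% of trials with no beer difference, and exactly one beer then appears to work in 3% to 25%, against 2% with no trend.

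The size depends mostly on how large the shared fall is and whether it continues after phase 1. The documents give neither. Counselling that takes effect early and then holds gives the low end.

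Two stronger readings are not supported. The documents do not state that the test runs across visits. Nor is the beer-versus-beer comparison biased by counselling: a shared trend cancels from it, and its error rate stays near 5%. The risk is confined to the overall test and the within-beer changes being taken as evidence about a beer.

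**What to change.** In the Statistical analysis plan:

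- State that a beer effect is concluded only from the within-participant modified-minus-regular difference in change from phase baseline, with treatment order in the model.
- For skewed outcomes, name a method that keeps the order adjustment: transform the outcome, or take each person's phase 1 minus phase 2 difference in change and compare it between the two sequences with a rank-sum test.
- Do not use an overall test across visits as the gate to further comparisons.
- Report before-after changes within each beer with confidence intervals, as descriptive only, noting that they include the counselling given at every visit.

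The cost is SAP wording, with no extra visits, samples or participants. The sponsor gives up claims that a beer improved a measure from baseline.

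### The paired Wilcoxon follow-up tests for skewed outcomes carry no stated multiplicity correction, which can raise the false-positive rate if four or more visit values are compared

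*Combined protocol and SAP*

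**What the plan says.** The section on the statistical analysis plan says that the effects of the beers "will be evaluated by repeated measures ANOVA or the Friedman test, as appropriate". It then adds a second step: "When significant differences are detected, multiple comparisons will be made", and the means for that step are "the Bonferroni correction for normally distributed variables or the Wilcoxon test for paired samples for variables with a skewed distribution". The one threshold given for the analyses is P < 0.05 ("using a significance level of" that value).

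The section does not say how many repeated values enter each test, which pairs are then compared, or how a variable is judged to be skewed.

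Two other sections bear on the point. The visit schedule collects biochemical data six times after prescreening: at the start, middle and end of each phase. The primary objective is the effect "on glycemic metabolism (glucose, glycated hemoglobin, insulin and HOMA index"; triglycerides and C reactive protein are among the secondary outcomes.

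**The concern.** The sentence offers a correction (Bonferroni) and a test (Wilcoxon) as if they were alternatives of the same kind. An analyst who follows it literally will adjust pairwise p-values for normal variables and leave them unadjusted for skewed ones. Similar evidence could then be called significant for one outcome and not for another, only because of the shape of its distribution, and the data decide which route applies.

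Insulin and HOMA (primary objective), triglycerides and C reactive protein are plausible candidates for the skewed route. That is an assumption; the documents do not classify any variable.

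The preceding Friedman test protects the pairwise tests fully only when nothing changes. Counselling is given at prescreening and repeated at the visits of both phases, so a change over time that has nothing to do with the type of beer is credible. Such a change can make the Friedman test significant and open every remaining pair to a 5% test.

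**Working it through.** **The plan's own figure.** The plan gives no error rate for the follow-up comparisons. Its one calculated figure is the sample size, at two-sided 95% confidence and "90% of statistical power": 2 × (1.960 + 1.282)² × 16² / 12² = 2 × 10.511 × 1.778 = 37.4, against 37 stated. That calculation is for one comparison at 5% and allows for no pairwise family.

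**Inputs.** From the plan: the Friedman step, the 0.05 level, n = 37 before losses, and 44 × 0.75 = 33 completers at the stated 25% loss. Assumed: k, the number of repeated values (2, 3, 4 or 6); within-person correlation 0.6; and the pattern of true change.

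**Number of pairs.** m = k(k − 1)/2, so m = 1, 3, 6 and 15 for k = 2, 3, 4 and 6. The Bonferroni level is 0.05/m: 0.05, 0.0167, 0.0083 and 0.0033.

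**Simulation A.** n = 37, normal errors with unit variance, differing values shifted by 2 SD, 3,000 runs (2,000 for k = 6). Each entry is the chance of at least one false finding among the pairs that are truly equal, behind a Friedman test at 0.05 (no Friedman step for k = 2).

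| k | Pattern | Truly equal pairs | Wilcoxon at 0.05 | Wilcoxon at 0.05/m |
|---|---|---|---|---|
| 2 | no difference | 1 of 1 | 5.5% | 5.5% (nothing to correct) |
| 3 | none differ | 3 of 3 | 4.1% | 2.5% |
| 3 | one differs | 1 of 3 | 4.3% | 1.2% |
| 4 | none differ | 6 of 6 | 4.4% | 2.4% |
| 4 | one differs | 3 of 6 | 12.5% | 1.7% |
| 4 | two and two | 2 of 6 | 10.7% | 2.1% |
| 6 | none differ | 15 of 15 | 5.2% | 1.9% |
| 6 | one differs | 10 of 15 | 31% | 3.0% |

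The largest Monte Carlo standard error is about √(0.31 × 0.69 / 2000) = 1 percentage point.

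**Check by hand.** Once the Friedman test is passed because of a real change, q truly equal pairs tested at 5% give 1 − 0.95^q if independent: 9.8% for q = 2, 14.3% for q = 3 and 40.1% for q = 10. Pairs that share a visit are correlated, so the simulated 12.5% and 31% lie below the last two; the 10.7% agrees with 9.8% within simulation error. With three values, one real difference leaves a single equal pair, hence no inflation. Bonferroni limits the error to q × 0.05/m: 1.7% (2 of 6), 2.5% (3 of 6) and 3.3% (10 of 15), again in line with the table within simulation error.

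**Simulation B, closer to the trial.** n = 33, log-normal values, correlation 0.6, no difference between beers, and the same fall in both phases, reversed in the wash-out.

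- Four values (start and end of each phase, 2 of 6 pairs truly equal): about 7-10% uncorrected, 1.3-1.7% with Bonferroni.
- Six visits, full fall reached by mid-phase (7 of 15 pairs equal): 19% with a small fall and 23-26% with a larger one, against 1.3-2% with Bonferroni.
- Six visits, gradual fall (3 of 15 pairs equal): 9-13%, against about 1.2%.
- End-of-phase beer-versus-beer pair alone, behind the Friedman test: 3.3-5.5% with four values, 3.0-5.4% with six visits.

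**The case against.** The strongest reply has four parts.

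- The plan never says the Wilcoxon tests are unadjusted. The sentence may be a careless pairing of a correction with a test, and the 0.05 is inferred from the general significance level.
- Follow-up tests happen only after a significant Friedman test, which holds the error near 5% when nothing changes.
- The number of repeated values is not given. The sample size is built on the change in glucose between two arms, which suggests one contrast, where there is nothing to correct.
- With four values and an equal fall in both phases, one of the two truly equal pairs is start versus start, which is not an efficacy claim.

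All four are fair, and they limit the size of the problem. They do not remove it. If a correction was intended, the sentence still needs repair. The plan itself speaks of multiple comparisons, which a single contrast would not need, and six visits with biochemical data make four or six values a natural reading.

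A reader might infer that false positives for skewed outcomes are inflated under this plan whatever happens, or that the comparison of the two beers runs at 10-30% error. The documents support neither. The first needs four or more values with some true change; the second is contradicted by the 3-5% found for that pair. Nor is 1 − 0.95^15 = 53.7% the plan's error rate: it ignores the Friedman step and the correlation between pairs.

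**Conclusion.** The point stands in conditional form. That the correction is attached only to normal variables is plain from the text. Its consequence depends on what the plan leaves open:

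- **No inflation** with two or three values, or when nothing changes.
- **Inflation** with four or more values and some true change: about 7-12% for four values and 10-30% for six visits, against about 1-3% with Bonferroni.
- **Little effect on the main question:** the end-of-phase beer contrast alone stays at about 5%.

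Confidence in the reading of the text is high. Confidence in the size is limited, because the number of values, the correlation of 0.6 and the pattern of change are all assumed. The pattern matters most: for six visits, a gradual fall in place of an early one roughly halves the figure. The wording should be corrected, but the point does not threaten the trial's central comparison.

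**What to change.** State in the statistical analysis plan which visit values enter each overall test and which pairs are compared afterwards. State also that the paired Wilcoxon p-values carry the same Bonferroni correction as the comparisons of normal variables, or that Holm is used. This takes a sentence or two, and the cost is slightly larger p-values for skewed outcomes.

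An optional alternative is to pre-specify a single end-of-phase beer contrast for every outcome, with skewed variables on the log scale, so that no pairwise family arises. That is a design preference and is not needed to repair this point.
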